### **3.5. Duration of Follow Up**

The duration of the follow up period will be 48 months.

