#### 5.5.1 Study Drug Discontinuation

Treatment with Nivolumab will be discontinued if treatment cannot be tolerated (toxicity), due to disease progression, or for whom treatment could not be resumed after non-toxicity related hold (see Section 5.5).

Those subjects who discontinue from treatment regardless of reason will be followed as described in section 6.1. Time and Events Schedule.

See Section 7.2 for handling of participants who withdraw from the study.

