## **6. STUDY SCHEDULE**

### **6.1. Time and Events Schedule**

**Table 3.** Time and Events Schedule is on the following page.

	Screening	Treatment Cycle (4 Week Cycle) a												Follow up (months) k										End of Treatment (EOT)/Withdrawal m
														M1 Post-Scans	Every 3 months from last Infusion x 1 year				Every 6 months subsequently x2 years				Final Year	
															M3	M6	M9	M12	M18	M24	M30	M36	M42 and M48	
	28 Days*	1	2	3	4	5	6	7	8	9	10	11	12		M3	M6	M9	M12	M18	M24	M30	M36	M42 and M48	
Informed Consent	X																							
History and Physical Exam b	X	X	X	X	X	X	X	X	X	X	X	X	X	x	X	X	X	X	X	X	X	X	X	X
Vital Signs	X	X	X	X	X	X	X	X	X	X	X	X	X	X	X	X	X	X	X	X	X	X	X	X
Beta HCG Pregnancy Test c	X	X	X	X	X	X	X	X	X	X	X	X	X											
ECOG Performance Status	X	X	X	X	X	X	X	X	X	X	X	X	X	X	X	X	X	X	X	X	X	X	X	X
Laboratory Assessments d	X	X	X	X	X	X	X	X	X	X	X	X	X	X	X	X	X	X	X	X	X	X	X	X
Cross-sectional imaging, including at minimum chest, abdomen and pelvis e	X							X						X		X		X	X	X	X	X	X	X l
AE Assessment		Assessed at every visit																						
Research blood sample collection f	X j	X j			X			X			X			X		X		X	X	X				X
CTC Analysis g	X j	X j			X									X										
Quality of Life Assessment (Appendix #1)		X	X	X	X	X	X	X	X	X	X	X	X			X		X	X	X	X	X	X	X
Nivolumab Therapy		X	X	X	X	X	X	X	X	X	X	X	X											
Archived tissue request	X																							

\*Screening period is a total of 28 days; Screening labs that are performed within 7 days prior to C1D1 do not need to be repeated

a. Treatment may be administered with a window of ± 7 days.

b. Visits may be performed with a window of ± 14 days. Long-term follow up may be discontinued once the primary end point is assessed and met.

c. If female of childbearing potential, a pregnancy test will be required at screening visit and prior to the start of each cycle of study drug.

d. Laboratory Assessments:

- Hematology labs to include hemoglobin, hematocrit, red blood cell count, white blood cell count, platelets (direct platelet count), as well as total and differential CBC counts. The CBC differential includes enumeration of neutrophils, lymphocytes, eosinophils, monocytes, basophils and any abnormal blood cells noted in the differential.

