  - Chemistry laboratory analysis includes albumin, urea or BUN, creatinine, ALT, AST, LDH, serum alkaline phosphatase, total bilirubin, TSH, glucose, total protein, sodium, potassium, chloride, and CO2.
  - Hematology, chemistry and endocrine laboratory analysis to be performed within 7 days prior to each Nivolumab treatment
- e. CT or PET/CT imaging will be performed after the 6th infusion (prior to treatment cycle 7) and after the 12th infusion (prior to month 1 Follow-up). All scans during the 24 month follow-up period should be performed 6 months after last previous scan and at the discretion of the treating physician. After 24 months of follow-up, scans will be performed per standard of care or the discretion of the treating physician. If a participant discontinues treatment for any reason, including disease progression, scans and visits will resume at the next scheduled timepoint as indicated in the table.
- f. Research blood samples are optional for subjects. Samples will be drawn any time within the 28 day screening period up until pre-dose C1D1, every 3 months during nivolumab therapy, and then every 6 months thereafter through Month 24 of follow up.
- g. CTC analysis samples are optional for subjects. Samples will be drawn any time within the 28 day screening period up until pre-dose C1D1, at 3 months, and 12 months.
- h. Patients will be monitored for local or regional recurrence based on physical examination at their treatment visits and cross-sectional imaging.
- i. Screening labs and physical performed as part of screening can be used to satisfy Cycle 1 Day 1 requirements if completed within 7 days of first treatment
- j. Research Study samples and CTC Analysis can be collected any time during the screening period up until pre-dose Treatment Cycle 1.
- k. For the follow up visits occurring after the M1 visit can occur  $\pm 6$  weeks
- l. Per standard of care, performed if clinically indicated. Or if scans were done within 8 weeks, reports and images will be obtained.
- m. For patients who discontinue treatment due to disease progression, they will be followed only for survival every 3 months starting from the EOT visit. If information is available on subsequent treatments, this will be collected.

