## **7. STUDY PROCEDURES AND EVALUATIONS**

### **7.1. Procedures by Visit**

The Time and Events Schedule (Table 3) summarizes the frequency and timing of various measurements.

Eligible patients will be consented, enrolled and treated on study. Patients will receive nivolumab 480 mg as a flat dose IV over at least 30 minutes every 4 weeks for a total of 12 doses over the course of 48 weeks. During these 48 weeks, patients will be seen in clinic monthly prior to each infusion for interval history and physical examination, with routine bloodwork obtained including a CBC, comprehensive metabolic panel, TSH and LDH. Subsequently, patients will be seen on an every 3 month basis through month 24 of the study, and every 6 months through month 60 of the study. Cross-sectional imaging including a chest, abdominal and pelvic CT imaging (or PET/CT imaging) will be performed after the 6th infusion (prior to the start of Cycle 7) and after the 12th infusion (prior to month 1 Follow-Up). All scans during the 24 month follow-up period should be performed every 6 months after the last previous scan and at the discretion of the treating physician. After 24 months of follow-up, scans will be performed per standard of care or the discretion of the treating physician. If a participant discontinues treatment for any reason, including disease progression, scans and visits will resume at the next scheduled timepoint as indicated in in Section 6.1. Participants who discontinue treatment due to disease progression will have an End of Treatment (EOT) visit and will be followed for only survival every 3 months from that visit (see Section 6.1). An optional tissue sample may be collected at the time the time of recurrence, if patients have agreed and a biopsy is being performed.

Preserving quality of life is a critical consideration when developing therapies for conditions in which majority of the patients have favorable outcomes. This is true for patients with early stage melanoma, as nearly 70% of them are cured by surgical excision alone. During treatment, we will evaluate the quality of life prior to each treatment. During follow-up, we will evaluate quality of life every 6 months using the Functional Assessment of Cancer Therapy – Melanoma (FACT-M) quality of life instrument.

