### **7.2 Withdrawal of Consent**

Participants who request to discontinue study drug or for whom study drug must be discontinued will remain in the study and must continue to be followed for protocol-specified follow-up procedures (see Section 6.1). The only exception to this is when a participant specifically withdraws consent for any further contact. Participants should notify the investigator of the decision to withdraw consent from future follow-up in writing, whenever possible. The withdrawal of consent should be explained in detail in the medical records by the investigator, as to whether the withdrawal is from further treatment with the study drug or also from study procedures and/or post-treatment study follow-up, and entered on the appropriate CRF page. In the event that event vital status (whether the participant is alive or dead) is being measured, publically available information should be used to determine vital status only, as appropriately directed in accordance with local law.

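### After treatment stops for progression, the plan says both that scans continue and that only survival is followed, so distant metastases may be missed; footnote b also leaves the end of follow-up open

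*Combined protocol and SAP*

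**What the plan says.** The schedule in Section 6.1 gives two rules for a patient who stops treatment because of progression.

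- Footnote e: "If a participant discontinues treatment for any reason, including disease progression, scans and visits will resume at the next scheduled timepoint".
- Footnote m, attached to the End of Treatment column: "For patients who discontinue treatment due to disease progression, they will be followed only for survival every 3 months starting from the EOT visit". It adds only that information on later treatments is collected if available.

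Section 7.1 restates the footnote e rule, and its next sentence says that participants who stop for progression "will be followed for only survival every 3 months from that visit".

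Two other sections touch the point. Section 5.5.1: "Those subjects who discontinue from treatment regardless of reason will be followed as described in section 6.1". Section 7.2 says that participants who come off drug "will remain in the study and must continue to be followed for protocol-specified follow-up procedures", and again points to 6.1.

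DMFS and OS are secondary endpoints (2.3). Section 9.1.2 takes the DMFS event to be a diagnosis of metastatic disease; death is not named as an event, and no censoring rule for DMFS is given.

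On the length of follow-up, Section 3.5 states "The duration of the follow up period will be 48 months", and 7.1 runs visits to study month 60. Footnote b says "Long-term follow up may be discontinued once the primary end point is assessed and met".

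**The concern.** Footnotes e and m both name progression, so neither can be read as the general rule with the other as its exception. Five centers enroll, and each could follow a different rule while complying with the protocol.

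The endpoint exposed is DMFS. A local or regional recurrence is progression but not a DMFS event, so such a patient is still at risk for DMFS when follow-up shrinks to survival contacts. The loss of information is triggered by relapse. It is therefore plausibly informative, and it pushes the DMFS estimate upward. It may also differ by site.

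Footnote b raises a second, separate question: whether the length of OS and DMFS follow-up could depend on how the primary analysis turned out.

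**Working it through.** The plan gives no expected number of on-treatment recurrences, so there is no figure of its own to reproduce here. The evaluable sample size of 63 does not depend on these rules.

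**1. What each rule collects after a loco-regional recurrence on treatment**

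| Item | Footnote e, 7.1 first sentence | Footnote m, 7.1 next sentence |
|---|---|---|
| Scheduled scans and visits | yes | no |
| Date of later distant metastasis | yes | not planned |
| Death | yes | yes, 3-monthly contact |
| RFS event | already recorded | already recorded |

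Nothing elsewhere recovers the distant event under footnote m. Section 5.5.1 sends the reader back to 6.1, which holds both rules. Section 7.2 allows public sources for vital status only. The DMFS definition does not count death, so a later melanoma death does not stand in for the missed metastasis.

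**2. How many patients are exposed**

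Inputs: 24-month RFS of 0.70 or 0.85 (9.3), 73 enrolled (9.3), 48 weeks of treatment (3.4). Constant hazard is assumed.

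- Treatment period: 48 × 7 / 30.4375 = 11.04 months.
- Risk of recurrence on treatment: 1 − S^(11.04/24).
- S = 0.85: 1 − 0.85^0.460 = 0.072, or 5.3 of 73.
- S = 0.70: 1 − 0.70^0.460 = 0.151, or 11.0 of 73.

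Expected recurrences by 24 months are 73 × 0.15 = 10.95 and 73 × 0.30 = 21.9, so roughly half fall in the treatment period. Twelve doses at 4-week intervals put the last dose at week 44; counting only to then gives 4.8 and 10.2. These counts treat every RFS event as a recurrence, so they are slightly high if some are deaths.

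**3. How many distant events could be missed**

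The loco-regional share and the proportion later becoming distant are not in the documents. Assume 30–60% and one half.

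- Low: 5.3 × 0.30 × 0.5 = 0.8.
- High: 11.0 × 0.60 × 0.5 = 3.3.

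That is about 1 to 3 events, or 1.1% to 4.5% of 73.

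**4. What this does to DMFS**

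Those percentages are close to a ceiling. They apply only if the affected patients are carried as free of distant metastasis throughout. If they are censored at recurrence, they leave the Kaplan-Meier risk set and the bias is smaller. A simulation with the inputs above used times from first dose, ignored deaths, and assumed a mean delay from loco-regional to distant recurrence of 6–18 months. It gave an upward bias of 0.5 to 3.1 points at 24 months and 0.1 to 1.3 points at 59 months. True DMFS at 59 months stayed above 50% in every scenario, though only narrowly in the least favorable one, so the median was not reached with or without the missed events.

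**5. Footnote b, if *met* means trial success**

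- Full follow-up from first dose: 11.0 + 48 = about 59 months.
- The primary endpoint is evaluated at study month 48 after 24 months of accrual (9.4), so follow-up then runs from 24 months (last patient) to 48 months (first patient).
- Loss if follow-up stops there: 59 − 48 = 11 to 59 − 24 = 35 months per patient.

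For scale, take 5-year survival of 70–80% (figures cited in 1.2.1 for stages IIB and IIA) and constant hazard. Median OS is then 60 × ln 2 / (−ln S) = 117 to 186 months, so it would not be reached with full follow-up either.

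**The case against.** The strongest reply is that the consequence is small. DMFS is a descriptive secondary endpoint with no hypothesis or decision rule. The stated objective is its median, which is unlikely to be reached. Section 9.1.2 names only OS and RFS for Kaplan-Meier estimation, so a rule censoring DMFS at loco-regional recurrence is the reviewer's supposition. Footnote e, 5.5.1 and 7.2 can all be taken to favor continued follow-up, in which case nothing is lost. All of this stands, and it limits the severity. It does not remove two opposite instructions for the same patients.

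Three stronger readings are tempting and are not supported:

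- **That OS is also under-ascertained.** Footnote m keeps survival contact every 3 months, more often than the 6-monthly visits after M12, and 7.2 adds public sources for vital status. The contradiction loses no deaths.
- **That footnote b ends follow-up because the trial succeeded.** It says *may*, and *met* is undefined. It could mean trial success or a patient reaching the endpoint; the second meaning would itself conflict with footnote m. Even if it means success, stopping is administrative censoring. It costs precision; it does not miss deaths within follow-up and is not a bias in itself.
- **That DMFS is overstated by up to 5 points.** This rounds up 4.5, combines the null RFS with the highest assumed loco-regional share, and divides by 73 as if no one left the risk set.

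Nor do the documents show that loco-regional relapse carries the highest risk of distant spread. The argument needs only that such patients remain at risk.

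**Conclusion.** The point holds as a contradiction in the follow-up rules that can cause distant metastases to be missed for DMFS, with a plausible upward bias and ascertainment that may differ by site. About 5 to 11 of 73 patients fall under the conflicting rules, at constant hazard and 24-month RFS of 85% to 70%. About 1 to 3 distant events could be missed under the assumed 30–60% loco-regional share with half later distant. The Kaplan-Meier bias is probably smaller than those events divided by 73. Primary RFS, OS ascertainment and sample size are untouched by it. Footnote m covers only patients who stop treatment for progression; no separate rule is given for recurrence after the twelfth dose.

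Footnote b is a separate ambiguity that conflicts with 3.5. If it means trial success, the length of OS and DMFS follow-up depends on the primary result and precision is lost. Should fix.

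**What to change.** 1. Reconcile footnotes e and m and the two sentences of 7.1 so that one rule applies. Which visit and scan schedule to keep is for the sponsor and investigators to decide.
2. Whichever rule is kept, after a non-distant recurrence record the date and site of first distant metastasis, taken from routine-care reports, and vital status at the contacts already planned, through the planned follow-up. Apply the same collection to recurrences after treatment is complete.
3. Reconcile footnote b with 3.5 so that the end of OS and DMFS follow-up does not depend on the primary result. Removing the sentence or defining *met* accordingly would both serve.

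The cost is a short amendment and a small addition to the case report form (date and site of first distant metastasis). No added procedures or contacts are needed during treatment or follow-up, and the 48 months are already planned. It is better done early, because unrecorded metastasis dates may be hard to recover later.

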## **7. STUDY PROCEDURES AND EVALUATIONS**

### **7.1. Procedures by Visit**

The Time and Events Schedule (Table 3) summarizes the frequency and timing of various measurements.

Eligible patients will be consented, enrolled and treated on study. Patients will receive nivolumab 480 mg as a flat dose IV over at least 30 minutes every 4 weeks for a total of 12 doses over the course of 48 weeks. During these 48 weeks, patients will be seen in clinic monthly prior to each infusion for interval history and physical examination, with routine bloodwork obtained including a CBC, comprehensive metabolic panel, TSH and LDH. Subsequently, patients will be seen on an every 3 month basis through month 24 of the study, and every 6 months through month 60 of the study. Cross-sectional imaging including a chest, abdominal and pelvic CT imaging (or PET/CT imaging) will be performed after the 6th infusion (prior to the start of Cycle 7) and after the 12th infusion (prior to month 1 Follow-Up). All scans during the 24 month follow-up period should be performed every 6 months after the last previous scan and at the discretion of the treating physician. After 24 months of follow-up, scans will be performed per standard of care or the discretion of the treating physician. If a participant discontinues treatment for any reason, including disease progression, scans and visits will resume at the next scheduled timepoint as indicated in in Section 6.1. Participants who discontinue treatment due to disease progression will have an End of Treatment (EOT) visit and will be followed for only survival every 3 months from that visit (see Section 6.1). An optional tissue sample may be collected at the time the time of recurrence, if patients have agreed and a biopsy is being performed.

Preserving quality of life is a critical consideration when developing therapies for conditions in which majority of the patients have favorable outcomes. This is true for patients with early stage melanoma, as nearly 70% of them are cured by surgical excision alone. During treatment, we will evaluate the quality of life prior to each treatment. During follow-up, we will evaluate quality of life every 6 months using the Functional Assessment of Cancer Therapy – Melanoma (FACT-M) quality of life instrument.

### **7.2 Withdrawal of Consent**

Participants who request to discontinue study drug or for whom study drug must be discontinued will remain in the study and must continue to be followed for protocol-specified follow-up procedures (see Section 6.1). The only exception to this is when a participant specifically withdraws consent for any further contact. Participants should notify the investigator of the decision to withdraw consent from future follow-up in writing, whenever possible. The withdrawal of consent should be explained in detail in the medical records by the investigator, as to whether the withdrawal is from further treatment with the study drug or also from study procedures and/or post-treatment study follow-up, and entered on the appropriate CRF page. In the event that event vital status (whether the participant is alive or dead) is being measured, publically available information should be used to determine vital status only, as appropriately directed in accordance with local law.

### **7.3 Lost to Follow Up**

All reasonable efforts must be made to locate participants to determine and report their ongoing status. Lost to follow up is defined by the inability to reach the subject after a minimum of 3 documented phone calls, texts, or emails as well as lack of response by the participant to 1 registered mail letter. All attempts should be documented in the participant's medical records. If it

is determined that the participant has died, the site will use permissible local methods to obtain the date and cause of death.

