#### **4.3 Strategies for Recruitment and Retention**

Potential subjects with Stage IIB and IIC melanoma will be identified by the examining physician at all sites and referred for evaluation by the principal investigator or one of the co-investigators.

The majority of completed and ongoing melanoma adjuvant clinical trials in the US have involved patients with higher risk stage III disease who are co-managed by medical oncologists, surgical oncologists and dermatology. The enrollment and accrual for these trials were typically driven by medical oncologists with longstanding referral patterns, well-established collaborative groups, and occurred at highly developed Centers of Excellence for melanoma care.

The trial we are proposing is distinct from other adjuvant melanoma trials in that the patients we will enroll are commonly managed primarily by dermatologists and/or surgical oncologists, with less common involvement of medical oncology. Many of these patients never see a medical oncologist unless they develop metastatic disease. Thus, the established mechanisms for the conduct of adjuvant clinical trials in melanoma are not sufficient for this study, and new mechanisms must be put in place to ensure successful accrual. The centers selected for participation in this trial have established melanoma disease management teams that will allow prospective identification of potential candidates by dermatology or surgical oncology, with referral to medical oncology when appropriate. Surgical oncology champions have been identified at each institution to assist with patient recruitment and enrollment.

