### **9.3. Sample Size Considerations**

Based upon recent retrospective analyses, the 24 month recurrence free survival rate for our patient population is 70%. To demonstrate a 50% improvement in the 24 month recurrence free survival rate (0.70 vs 0.85), with power of 0.90, alpha 0.05 using one arm non-parametric survival (one-sided) test, we will require enrollment of 63 evaluable patients. To account for potential loss to follow up of 15%, our target number of enrolled subjects is 73. We will require 24 months of follow-up for all patients for evaluation of the primary endpoint.

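### Section 7.3 lets a patient be coded as lost with no step to obtain recurrence status from treating clinicians, and 9.1.2 has no censoring rule or check for informative loss

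*Combined protocol and SAP*

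**What the plan says.** Section 7.3 opens with a general duty to make reasonable efforts to find participants and report their ongoing status. It then gives the operative rule: "Lost to follow up is defined by the inability to reach the subject after a minimum of 3 documented phone calls, texts, or emails", together with no reply to one registered letter. Every contact in that rule is with the participant. The only outcome with its own retrieval instruction is death, and it is conditional: once it "is determined that the participant has died, the site will use permissible local methods to obtain the date and cause of death". Section 7.2, on withdrawal of consent, adds that "publically available information should be used to determine vital status only".

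Section 4.3 describes the population: "the patients we will enroll are commonly managed primarily by dermatologists and/or surgical oncologists, with less common involvement of medical oncology".

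Section 9.3 sizes the trial "with power of 0.90, alpha 0.05 using one arm non-parametric survival (one-sided) test, we will require enrollment of 63 evaluable patients", for 0.70 against 0.85. It adds: "To account for potential loss to follow up of 15%, our target number of enrolled subjects is 73". It also requires 24 months of follow-up for all patients, and does not define evaluable.

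Section 9.1.2 estimates RFS by Kaplan-Meier and counts documented recurrence only. Section 2.2 counts progression or death. Neither says when a lost patient is censored, and no sensitivity analysis for loss is planned.

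**The concern.** Recurrence is the main component of the primary endpoint. A patient who recurs, is treated elsewhere and stops answering can be coded as lost under 7.3 without anyone asking the clinician who knows the outcome. Kaplan-Meier then treats that patient as having the same future risk as those still under observation. Dropping the patient as not evaluable has a similar effect.

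The test compares one arm with a fixed 70%, so there is no control arm in which the same loss could offset the bias. Any excess of recurrence among the lost raises estimated RFS and the chance of declaring an inactive drug successful.

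**Working it through.** **Plan's own figure (9.3).** Inputs: p0 = 0.70, p1 = 0.85, one-sided alpha 0.05, power 0.90.

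n = [(1.645·√(0.70·0.30) + 1.282·√(0.85·0.15)) / 0.15]² = 65.2. The arcsine form gives 64.7 and the log-log form 64.9. Normal-approximation power at 63 is 88.9%. The stated 63 is therefore close, and the sample size is not the problem here. Enrolment: 63 × 1.15 = 72.45, so 73. Loss at the planned rate: 0.15 × 73 = 10.95, so 11 patients.

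**If lost patients are excluded.** Let q be the true 24-month RFS among the 11 lost (an assumption), with 70% true overall:

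RFS in the 62 retained = 1 − [73 × 0.30 − 11(1 − q)] / 62

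- q = 0.70: 1 − 18.6/62 = 70.0%
- q = 0.50: 1 − 16.4/62 = 73.5%
- q = 0.30: 1 − 14.2/62 = 77.1%
- q = 0: 1 − 10.9/62 = 82.4%

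With 63 evaluable, significance needs about 0.70 + 1.645·√(0.21/63) = 79.5% observed (51/63 = 81.0% by the exact binomial).

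**If lost patients are censored in Kaplan-Meier.** Simulation assumptions:

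- Exponential recurrence in all 73, with 24-month RFS of 70%.
- k recurrers, drawn at random, are censored at their own recurrence.
- The other 11 − k are drawn from everyone else and given uniform loss times over 24 months. A recurrence before the loss time counts as an event.
- Success means the one-sided 95% log-log lower limit at month 24 exceeds 70%. The plan does not name the transformation.

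The last column gives each hidden recurrer a one-half chance of being found as a death before month 24 and counted under 2.2.

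| Left at an untraced recurrence (k of 11) | Mean estimated RFS | Type I error | Type I error, half found as deaths |
|---|---|---|---|
| 0 | 70.0% | 4% | – |
| 2 | 72.4% | 9–10% | 6% |
| 3 | 73.6% | 14% | 8% |
| 6 | 77.3% | 34–35% | 14% |

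**Sensitivity to the loss model.**

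- If the other 11 − k lost patients were all recurrence-free to month 24, type I error is about 9% at k = 3 and 29% at k = 6.
- If lost patients have a true 24-month RFS of 50% or 30% but leave at random times rather than at recurrence, it is 6.8% or 10.3%.
- With an untransformed Greenwood limit, the error with non-informative loss is already between 6% and 7%.
- With recurrence status fully traced in all 73, mean RFS is 70.0% and type I error 4.8%.

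**The case against.** Several points on the other side stand.

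- **Tracing is not barred.** A reader might infer that 7.3 rules out recurrence tracing, or that a lost patient can re-enter the analysis only as a death. The general duty covers ongoing status, the contact count is a minimum, and 2.2 does not restrict who documents a progression. What is missing is a named step and source, so sites may differ.
- **Deaths are not systematically traced.** A reader might combine 7.2 and 7.3 into a contrast of deaths traced and recurrences ignored. Section 7.3 seeks death details only once a death is known, and the public-record search belongs to withdrawal of consent. Deaths that are found also work against the inflation under 2.2, though not under the recurrence-only wording of 9.1.2.
- **15% is a planning allowance**, not an accepted limit on loss.
- **Informative loss is assumed.** Patients are seen monthly on treatment and then every three months through month 24, with scheduled imaging (7.1). Section 4.3 concerns recruitment, says the centres' melanoma teams work with dermatology or surgical oncology, and implies that metastatic disease brings patients to medical oncology. Each point makes silent departure at recurrence less likely, but none excludes it.
- **Some material is not visible.** Consent pages were removed and 11.3 mentions a Manual of Procedures, so a records release or tracing procedure may already exist.

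None of this supplies the missing censoring rule or sensitivity analysis in section 9.

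**Conclusion.** The gap is real but limited. The plan names no route to recurrence status for a patient who stops responding, and gives neither a censoring rule nor a check for informative loss. If loss is unrelated to recurrence there is no bias, and type I error is about 4%. With 11 of 73 lost and a true RFS of 70%, three untraced recurrences raise it to about 14% and six to 34–35%. If half of those patients are found as deaths and counted, the figures are about 8% and 14%.

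A reader might go further and infer that the trial is likely to declare an inactive drug effective. The documents do not support that: they give no recurrence rate among lost patients, and even at k = 6 the mean estimate of 77.3% stays below the roughly 79.5% needed with 63 evaluable. This is a worthwhile, inexpensive improvement to how the primary endpoint is ascertained and analysed.

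**What to change.** **Section 7.3.** Before a patient is coded as lost, and at month 24 for anyone not seen, request recurrence status, recurrence date and last recurrence-free date from the treating dermatologist, surgeon or oncologist. Use a records release signed at entry if the consent does not already provide one.

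**Section 9.1.2.**

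- Reconcile the RFS event with 2.2, as recurrence or death.
- Define evaluable.
- Censor untraced patients at their last disease assessment.
- Keep every known death as an event. Counting a death after loss only where recurrence had been traced to the same date would discard known 2.2 events and raise RFS.
- Report beside the primary result a tipping-point analysis: how many lost patients must have recurred at their loss date before the lower one-sided 95% limit for 24-month RFS falls to 70%.

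**Cost.** Records requests for about 11 patients at the planned loss rate, possibly one consent line, and one further analysis. The RFS figure may be slightly less favourable. Treatment and sample size do not change.
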